9.2.10 Week 25 (Post-Treatment Response) Procedures

Subjects will report to this visit fasted. The following procedures will be performed at the Week 25 visit:

- [REDACTED]
- Record concomitant medications
- Record new and/or changes to AEs
- Obtain 10-hour fasted clinical laboratory samples for the following:
 - Chemistry
 - INR
 - Lipid panel
 - Lipase
 - C4 and serum bile acids
 - PK sample
 - ADAs
 - NAbs
 - ELF panel

- Pro-C3

■ [REDACTED]

■ [REDACTED]

■ [REDACTED]

Results for ALT, AST, Total Cholesterol, LDL, HDL, and triglycerides are blinded to the site and sponsor.

Before clinic discharge:

- Schedule Week 30 (End of Study) visit

Lipid-Monitoring Assessment:

The third-party Medical Monitor will evaluate LDL-C (refer to [Section 9.4.14](#)). Subjects who have an LDL-C value of > 100 mg/dL, and > 15 mg/dL above their Day 1 value at Week 25 will be re-assessed at Week 30.

9.2.11 Week 30 (End of Study) Procedures

This visit will be performed 6 weeks after the EOT visit. Subjects will report to this visit fasted.

- Measure body weight, BMI, and waist circumference
- [REDACTED]
- Obtain 12-lead ECG (after subject has been supine for at least 5 minutes)
- Measure vital signs (including temperature, respiratory rate, and seated blood pressure and pulse)
- Obtain an MRI-PDFF assessment
- Record concomitant medications
- Record new and/or changes to AEs
- Obtain 10-hour fasted clinical laboratory samples for the following:
 - Chemistry
 - CBC
 - HbA1c
 - Insulin level
 - HOMA-IR calculation
 - [REDACTED]
 - INR

- PK Sample
- Lipid panel
- Lipoprotein particles
- Lipase
- C4 and serum bile acids
- ADAs
- NAbs
- ELF panel
- Pro-C3

Results for ALT, AST, Total Cholesterol, LDL, HDL, and triglycerides are blinded to the site and sponsor.

- Urine pregnancy test (all female subjects of childbearing potential).
- Obtain urine sample for urinalysis
- Collect old rosuvastatin bottles/diary and conduct reconciliation (***only for subjects who were on statin therapy at Baseline and continued on rosuvastatin after EOT visit***)

Lipid-Monitoring Assessment:

For subjects who were identified at Week 25 as needing re-assessment of LDL-C at Week 30, the third-party Medical Monitor will evaluate LDL-C results to assess the need to schedule a 4 week LDL-C safety follow up visit to confirm their LDL-C value has returned ≤ 100 mg/dL or ≤ 15 mg/dL above their Day 1 value (refer to [Section 9.4.14](#)).

9.2.12 Lipid Monitoring Assessment 4 Week Follow up Visit Procedures

This visit will be performed 4 weeks after the EOS visit. The following procedures will be performed at this visit:

- Record concomitant medications
- Record AEs

- Obtain blood for 10-hour fasted laboratory sample collection for:
 - Chemistry
 - Lipid panel

9.2.13 Monitoring of Anti-Drug Antibody Response

Subjects maybe contacted to participate in additional optional follow-up visits, if necessary, to monitor anti-drug antibody (ADA) responses.

9.3 Concomitant Medications

Any medication taken at least once within 42 days prior to Screening Visit and during the study period as well as the reason for use will be recorded in the source documents and the CRFs. Subjects should refrain from the use of any new prescription medications or products or changes in the dose or frequency of existing therapies from Screening to Day 1 until EOS.

The Sponsor Medical Monitor or designee should be informed of any changes or addition of prohibited medications during this time period.

9.3.1 Prohibited Medications

- Investigational agents, other than aldafermin/matched placebo, or devices for any indication. These agents must also have been discontinued prior to Screening per exclusion criterion #24.
- Any other lipid lowering agents or combination preparation of statins (other than ezetimibe when used as a second-line lipid management therapy per [Section 9.4.14](#), or one of the approved statin therapies listed in inclusion criterion #6) including:
 - Cholestyramine, colestevam, PCSK9 inhibitors (evolocumab or alirocumab), colestid, niacin, fibrates, fenofibrates, fish oil from Day -42 onward through the end of the study.
- Agents used for the treatment of any condition listed in the exclusionary enrollment criteria (see [Section 8.2](#)) from Day -42 onward through the end of the study.
- Weight loss medications, including orlistat, phentermine, topiramate, qsymia, lorcaserin hydrochloride, naltrexone hydrochloride, liraglutide, benzphetamine, diethylpropion, phendimetrazine from Day -42 onward through the end of the study.
- Contraindicated medications according to the rosuvastatin package insert, [Appendix 6](#) including; cyclosporine, gemfibrozil, protease inhibitors (atazanavir, ritonavir, lopinavir, simeprevir), coumarin anticoagulants, fenofibrates, niacin, colchicine, from Day -42 onward through the end of the study.

- Contraindicated medications according to the ezetimibe package insert, [Appendix 7](#) including; cyclosporine, fenofibrate, cholestyramine, coumarin anticoagulants, from Day -42 onward through the end of the study.
- Known hepatotoxic agents (refer to [Appendix 9](#)) For subjects who have been on stable therapy with no related hepatotoxicity, the MM may be contacted to assess the medical context and eligibility of the subject, from Day -42 onward through the end of the study.
- This list of prohibited medications along with [Appendix 6](#), [Appendix 7](#), and [Appendix 9](#) are not an inclusive list. Investigator judgement must be used to justify initiating any study medication during the study. Use of allopurinol to treat gout is allowed if there is no history of intolerance.

9.3.2 Restricted Concomitant Medications/Treatments:

- Statin Therapies: For statin experienced subjects only, the following daily dose of approved statin therapies are allowed if dosing is stable at least 3 months prior to Screening through Week 2:
 - Atorvastatin: ≤ 40 mg/day
 - Fluvastatin: ≤ 40 mg/day
 - Lovastatin: ≤ 40 mg/day (immediate release), ≤ 30 mg/day (extended release)
 - Pitavastatin: ≤ 2 mg/day
 - Pravastatin: ≤ 40 mg/day
 - Simvastatin: ≤ 40 mg/day
 - Rosuvastatin: ≤ 20 mg/day
- Other therapies for NAFLD or NASH require a stable regimen for at least 3 months prior to the Screening biopsy of record and throughout the study including:
 - Standard vitamin supplements
 - Vitamin E (>400 IU)
 - Pentoxifylline
- Diabetic medications:
 - Insulin: require stable dosing, defined as reasonable dose adjustments to maintain glucose control, for at least 3 months prior to Day 1
 - All other diabetic medications (except liraglutide which is prohibited): require a stable dose for at least 3 months prior to Day 1. The investigator may adjust diabetic medications as warranted based on clinical response/glucose control parameters throughout the study.

- Antibiotics (not listed in [Appendix 9](#)) use will be at the discretion of the principal investigator
- Procedural Medications including anti-anxiety medication for MRI scan, anesthetic or sedation (e.g., a benzodiazepine) for liver biopsy or for other minor (outpatient) procedures will be used at the discretion of the principal investigator
- Anabolic steroids; low levels of estrogen or testosterone as replacement therapies are allowed.

9.4 Clinical Evaluations

9.4.1 Alcohol Consumption

9.4.1.1 AUDIT-C

During Screening, clinical sites will implement the AUDIT-C, a 3-item alcohol screen that can help identify persons who are hazardous drinkers or have active alcohol use disorders (see [Appendix 8](#)). The AUDIT-C is scored on a scale of 0-12. Each AUDIT-C question has 5 answer choices. Points allotted are a = 0 points, b = 1 point, c = 2 points, d = 3 points, e = 4 points. In men a score of 4 or more is considered positive, optimal for identifying hazardous drinking or active alcohol use disorders. In women a score of 3 or more is considered positive.

9.4.1.2 History of Alcohol Consumption

Subjects will also be asked to report their history of alcohol consumption and will be excluded from study participation if they consume ≥ 21 units per week (males) or ≥ 14 units per week (females) for two years prior to enrollment and where a unit of alcohol is equivalent to a 12-ounce beer, 4-ounce glass of wine, or a 1-ounce shot of hard liquor.

9.4.1.3 PEth Screen

Subjects that present with a significant alcohol intake as measured by a phosphatidylethanol (PEth) level ≥ 200 ng/mL AND also have a positive AUDIT-C score ([Section 9.4.1.1](#)) will be excluded from the study at Screening.

9.4.2 Liver Biopsy

Subjects who meet the Screening criteria of an available liver biopsy tissue specimen within 6 months of Screening will not be required to undergo a new liver biopsy. For subjects who have participated in a prior study involving an investigational agent for NASH, the prior liver biopsy obtained within 6 months may be used only if the subject was treated with placebo. All other subjects will be required to undergo a liver biopsy per the study site's local standard-of-care procedure during the Screening period and prior to randomization. Sites should not perform a local reporting of the NAS or fibrosis score at either Screening or

Week 24 to the site in order to maintain the blinding of the primary endpoint. Tissue from all subjects will be collected, prepped and sent to the Central Study Pathologist for review for the absence/presence of NASH as defined in the Biopsy Manual. Liver biopsies with histologically confirmed NASH will be further assessed using the NAS established and validated by the NASH CRN (see [Appendix 1](#)). Liver biopsies will be assessed for degree of steatosis (0 – 3), lobular inflammation (0 – 3), hepatocellular ballooning (0 – 2), and fibrosis (0 – 4). The first three components will be added together to determine the NAS that ranges from 0 to 8. Liver biopsies with an NAS of <4 will be considered exclusionary. Subjects with liver biopsies with Stage 4 fibrosis, consistent with cirrhosis, will be excluded from this study. The Week 24 biopsy should be obtained \leq 7 days before last dose of aldafermin/matched placebo.

9.4.3 Magnetic Resonance Imaging (MRI)

All enrolled subjects will have a Baseline (from the Screening result) and EOT MRI of the liver to evaluate [REDACTED] liver fat. Subjects will have an MRI performed at Screening Day -28 and at Weeks 12, 24 (EOT), and 30 (EOS). MRI-PDFF will be reported on all MRI imaging scans. Scans should be performed at high field strength (3T preferred, 1.5T acceptable), without the administration of oral or intravenous contrast material. MRI examinations will include a six-echo gradient recalled [REDACTED]
[REDACTED]

The initial study MRI examination will be performed during the Screening period prior to randomization. An MRI-PDFF value of $\geq 8\%$ at Screening as assessed by the central radiology core is one of the inclusion criteria for the study. Therefore, for subjects who require a liver biopsy as part of the trial (for whom no recent liver biopsy is available), it is recommended that the liver biopsy be scheduled no sooner than 7 business days after (electronic) transmission of the screening MRI examination to the central radiology core to allow adequate time for processing and reporting of the result. The screening MRI-PDFF results will be reported to the individual site no more than 5 business days after the MRI examination is received. The Screening MRI result is valid for up to 8 weeks and may be used for a subject who is re-screened within that time frame. None of the on treatment or post treatment MRI results (other than incidental findings) will be provided to the sites. Week 24/EW/EOT MRI-PDFF should be performed before the last dose of aldafermin/matched placebo.

For both Screening and EOT/Early Withdrawal MRI examinations, subjects should consume nothing by mouth (NPO) for 4 hours prior to their MRI appointment. Medications and small amounts of water are acceptable.

Prior to MRI, all subjects should undergo safety assessment per institutional protocols and per the guidelines of the local Institutional Review Board. Subjects should be questioned regarding claustrophobia, pregnancy or potential pregnancy, size or weight exceeding the capabilities of the MRI system, metal implants, and other potential safety issues.

Detailed instructions for MRI procedures and provision of examination to a central reader will be presented in a separate MRI Manual.

9.4.4 Pharmacokinetic Blood Sample Collection and Processing

In all subjects, blood samples for PK analysis of aldafermin levels will be collected before dosing at study visits at [REDACTED]

The [REDACTED]

The window for sample collection for the pre-dose and 2-hour time points is ± 5 minutes.

[REDACTED] at the Day 1 and Week 24 visits at the following time points: pre-dose, 0.5, 1, 2, 4, 6, 8, 12, and 24 hours post-dose. The window for sample collection for the 0.5-hr through 8-hour time points is ± 5 minutes. The window for sample collection for the 12- through 24-hour time points is ± 30 minutes.

Processing, storage, and shipping instructions for these PK blood samples will be presented in the study Lab Manual.

9.4.5 C4 and Bile Acid Testing

C4 and bile acid testing will be collected at Day 1 and Weeks 2, 4, 8, 12, 18, 24, 25, and 30. In addition, for subjects participating in the optional PK sub-study, additional C4 will be tested at the same timepoints as the PK blood sample collections: Day 1 and Week 24 at pre-dose, and post-dose at 0.5, 1, 2, 4, 6, 8, 12, and 24 hours.

9.4.6 Biomarkers

Blood samples will be collected for ELF score, Pro-C3, [REDACTED] genetic biomarker including PNPLA3 will be collected as outlined in [Table 4](#).

9.4.7 Insulin/HOMA-IR

Insulin level and HOMA-IR will be evaluated at Day -42 (Screening), Day 1, Week 12, Week 24 and Week 30. Subjects will have fasted 10 hours.

9.4.8 Lipoprotein Particles

Lipoprotein particles, [REDACTED] will be tested on scheduled visits on Day 1 through Week 24 and on Week 30. Subjects will have fasted 10 hours ([Table 4](#)).

9.4.9 Clinical Laboratory Evaluations

Clinical laboratory evaluations will be collected as outlined in [Table 4](#). Blood and tissue samples will be collected and any remaining or back-up study samples may be used for future exploratory and biomarker analysis related to aldafermin treatment or metabolic diseases. The samples will be stored for up to 15 years.

Serum chemistry will include ALT, AST, ALP, bicarbonate, bilirubin (direct and total), BUN, calcium, chloride, creatinine, CK, GGT, glucose, HDL, LDL, lipase, phosphate, potassium, proteins (albumin, total protein), sodium, total cholesterol, and TG. Creatine Kinase will be collected at Day -42, Day 1, Weeks 12 and 24. Samples for analysis of ADAs, NAbs, and exploratory biomarkers will be collected. A blood sample for genetic biomarker testing will be collected pre-dose on Day 1. All NAB samples will be collected as scheduled, and analyzed only if necessary, based on ADA results.

Liver function tests, including AST, ALT, TBL and ALP, will be compared between Day -42 and Day -28 to assess whether there is worsening of liver disease during screening according to exclusion criterion [#6](#). An unscheduled visit may be necessary to confirm eligibility if the difference exceeds 35%. If performed, unscheduled visit results will be compared to the average of Day -42 and Day -28 results to determine if eligibility ranges (i.e., % agreement $\leq 35\%$) are met.

Processing, storage, and shipping instructions for the above will be presented in a separate Lab Manual.

9.4.10 12-Lead Electrocardiograms

12-lead ECGs will be performed after the subject has been supine for at least 5 minutes, and as outlined in [Table 4](#).

9.4.11 Vital Signs

Vital signs (including temperature, respiratory rate, and seated blood pressure and pulse) will be obtained at Screening and at all study visits as outlined in [Table 4](#). Seated blood pressure and pulse will be measured after the subject has been seated for at least 5 minutes.

9.4.12 Physical Examinations and RUQ Pain Assessment

[REDACTED]

Subjects will be weighed, BMI calculated, and waist circumference measured at Screening Day -42, Day 1, and Weeks 12, 24, and 30. Formal instructions for recording weight and measuring waist circumference will be provided to sites.

9.4.13 Local Injection-Site Symptom Assessments (LISSA)

Injection-site evaluation will be made and documented by the PI or clinic staff using a LISSA ([Appendix 2](#)).

LISSA evaluations are to be performed at each clinic visit from Day 1 through Week 24.

The LISSA is intended to be a “snapshot” of the ISRs at the time of clinic assessment. The LISSA is not intended to capture ISR data (frequency, severity, duration, etc.) in between clinic visits. As with any other potential AE, Investigator judgment should be used as to whether any ISR is recorded as an AE. Mild to Severe Reactions (LISSA Grades 1–3) are reported as AEs at the discretion of the investigator unless standard SAE criteria are met and then must be reported as an SAE. Life-threatening (LISSA Grade 4) meet SAE criteria and must be reported as such.

LISSAs may be performed if necessary and as clinically indicated by the PI to capture ISRs outside of the routine scheduled assessment time points.

The 2007 FDA Toxicity Grading Scale ([Appendix 2](#)) will be used to assess any ISRs ([U.S. Department of Health and Human Services 2007](#)). The documented record will include all of the symptoms, severity, and any local reaction (including pain, tenderness, redness, and swelling) and size of injection-site skin reactions identified and observed by the subject or clinic personnel. LISSA scores will be documented on the subject’s CRF.

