The potential therapeutic benefits of increased FGF19 pathway activity in metabolic disease and NASH is well documented in various animal models of disease. For example, aldafermin has been evaluated in various mouse animal models of NASH, and has demonstrated improvement in the histologic, biochemical, and fibrogenic biomarkers associated with NASH-related hepatic injury (Study 13-PD-NGM282-1007). Furthermore, aldafermin produced significant reduction in steatosis, inflammation, and ballooning in mouse models of NASH (Zhou 2017). Importantly, aldafermin is devoid of proliferative activity based on chronic evaluation in rodents and non-human primates that is a potential limitation of FGF19 as a therapeutic agent (Zhou 2014). Aldafermin was selected from more than 160 variants of human FGF19 that were screened to retain robust efficacy while lacking evidence of proliferative activity in db/db mice (Luo 2014, Zhou 2014, DePaoli 2019).

The safety, tolerability, pharmacokinetics (PK), and pharmacodynamics (PD) of aldafermin have been studied in a blinded, placebo-controlled, single-ascending-dose (SAD) and multiple-ascending-dose (MAD) study in normal subjects (Study 12-0101) and in subjects with T2D (Study 13-0102). Aldafermin was safe and generally well tolerated with dose-dependent mild to moderate injection-site reactions (ISRs), increases in total cholesterol and gastrointestinal (GI) symptoms (loose stools, abdominal cramping, nausea) the most common drug-related adverse events (AEs), which were observed mainly with higher doses. Dose-dependent significant reductions in serum C4 levels were also observed after administration of aldafermin in both populations supported target engagement and suppression of CYP7A1.

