2. The primary safety endpoint is frequency, severity, and timing of adverse events (AEs) and serious adverse events (SAEs). Safety and tolerability of aldafermin in subjects with NASH as a function of dose level after up to 24 weeks of treatment with aldafermin will be assessed.

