11.1 Definition and Grading Intensity of Adverse Events

An AE is defined as any untoward medical occurrence in a subject of clinical investigational participation administered a pharmaceutical product, whether or not considered drug related. A TEAE is an AE that is reported after a dose of study drug.

AEs include the following:

- Unfavorable changes in general condition
- Subjective or objective signs/symptoms
- Concomitant diseases or accidents
- Clinically relevant adverse changes in laboratory parameters observed in a subject in the course of a clinical study

AEs comprise all disturbances of general health status, subjective and objective disease symptoms (including laboratory abnormalities), and accidents observed in the context of a clinical trial, irrespective of a possible causal relationship with the administration of the trial substance. Events occurring in the framework of a clinical trial during drug-free and post-treatment periods or under placebo are also to be designated as AEs.

All AEs, regardless of how identified (e.g., volunteered, elicited, noted on physical examination), will be recorded throughout the study (i.e., from Screening until Follow-up).

Subjects will be followed for resolution of AEs, by querying the subjects for an ongoing AE until resolved or until any unresolved AEs are judged by the PI to have stabilized or if lost to follow-up. Resolution of all AEs will be promptly documented by the clinic on the subject's CRF.

Any pregnancy diagnosed during the study must be reported immediately to the PI and Sponsor, including pregnancy in female partners of male subjects. The pregnancy will be followed to term and/or outcome and this outcome must be reported to the Sponsor.

Pregnancy, in and of itself, is not regarded as an AE or SAE unless the birth results in a congenital anomaly/birth defect or there is suspicion that the study medication may have interfered with the effectiveness of a contraceptive medication or method.

The PI will rate the severity of AEs using the CTCAE v5 to grade the severity. Each CTCAE v5 term is a Medical Dictionary for Regulatory Activities (MedDRA) Lowest Level Term (LLT). The CTCAE displays Grades 1–5 with unique clinical descriptions of severity for each AE. Not all Grades are appropriate for all AEs. Therefore, some AEs are listed with fewer than five options for Grade selection. Grade 5 (Death) is not appropriate for some AEs and, therefore, is not an option.

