## 6.6 Injection Site Reactions

Injection site reactions will be evaluated using a local injection-site symptom assessment (LISSA). Frequency and percentage distribution of the severity of each pre-specified symptom (pain, tenderness, erythema/redness and induration/swelling) will be presented by treatment group for each visit.

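### AE recording of Grade 1–3 injection-site reactions is left to investigator discretion without criteria, so the AE-based primary safety endpoint can undercount them, and no planned LISSA table gives per-subject incidence

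*Protocol*

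**What the plan says.** Protocol Section 9.4.13 requires a LISSA at each clinic visit from Day 1 to Week 24, graded on the 2007 FDA scale in Appendix 2 and entered on the CRF. On whether a reaction also becomes an AE, it says: "As with any other potential AE, Investigator judgment should be used as to whether any ISR is recorded as an AE". Grade 1–3 reactions "are reported as AEs at the discretion of the investigator unless standard SAE criteria are met and then must be reported as an SAE"; Grade 4 must be reported as an SAE. The section describes LISSA as a snapshot that is not meant to capture what happens between visits. It allows extra assessments where the investigator sees a clinical need.

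Section 11.1 starts from a broad definition ("An AE is defined as any untoward medical occurrence in a subject") and continues: "All AEs, regardless of how identified (e.g., volunteered, elicited, noted on physical examination), will be recorded throughout the study". It does not mention injection-site reactions.

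Section 6.1 sets the endpoint: "The primary safety endpoint is frequency, severity, and timing of adverse events (AEs) and serious adverse events (SAEs"), with safety assessed by dose level. Section 5.2.2 lists "dose-dependent mild to moderate injection-site reactions (ISRs") among the most common drug-related AEs in healthy volunteers and subjects with type 2 diabetes.

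SAP 6.6 plans this for LISSA: "Frequency and percentage distribution of the severity of each pre-specified symptom", by treatment group and visit. SAP 2.2 puts unscheduled-visit data in listings and keeps them out of summaries. SAP 6.2 counts each subject once per preferred term, but only from events filed as AEs.

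**The concern.** Two recording rules apply to the same event. One says every AE is recorded. The other lets the investigator decide for most grades of one named reaction and gives nothing to decide by. The primary safety endpoint is built on the AE page, so what it reports about injection-site reactions depends on a choice the protocol leaves open.

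The question at stake is simple: in each dose group, what proportion of subjects had an injection-site reaction, and how bad was the worst one? In a three-dose study of a daily injection with a known dose-dependent local effect, a reader will expect that answer. If the TEAE tables depend on discretion and the LISSA tables do not count subjects over the whole treatment period, no planned table answers it cleanly.

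**Working it through.** The documents give no injection-site reaction rate, no AE filing rate and no power for safety, so there is no planned figure to reproduce. The check is mainly a comparison of text, followed by an illustration on assumed rates.

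**1. Do the two rules conflict?** Take Grade 3 pain in Appendix 2: use of a narcotic pain reliever, or daily activity prevented. That is an untoward medical occurrence on any ordinary reading of Section 11.1, so it must be recorded. Under Section 9.4.13, two sites could handle it differently and both comply. The conflict is clear at that end of the scale. At the other end (Grade 1 tenderness, mild discomfort on touch) it is arguable whether Section 11.1 is engaged.

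**2. Does the endpoint depend on the decision?** Yes. Section 6.1 names AEs and SAEs, not LISSA, and the SAP 6.2 tables draw on TEAEs only.

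**3. Does another source fill the gap?**

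| Source | Independent of the AE or investigator decision? | Covers time between visits? | Per-subject summary planned? |
|---|---|---|---|
| TEAE tables (SAP 6.2) | No | Yes, if filed | Yes |
| Scheduled LISSA (9.4.13, SAP 6.6) | Yes; 7 assessments: Day 1, Weeks 2, 4, 8, 12, 18, 24 | No | No; by symptom and visit |
| Extra LISSA (9.4.13, SAP 2.2) | No; investigator judgement | Yes, if done | No; listing only |
| Home diary (10.4.1) | Described as an administration diary; no symptom capture stated | – | No |

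No row is both independent of discretion and summarised per subject. Visit tables cannot be added up to give it. If an assumed 5% of a group showed one symptom at each of the 7 visits, the share ever affected could lie anywhere from 5% (the same subjects each time) to 7 × 5% = 35% (different subjects each time).

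**4. What could undercounting do?** Let p be the true proportion of subjects with a reaction, and s the probability that an affected subject is counted through the AE page. The recorded proportion is s × p. Assume s is equal in all arms, which blinding makes plausible. Every value of p and s here is an assumption.

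Each cell gives the recorded difference in percentage points, then nominal power at 38 per arm (two-sided 0.05):

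| True placebo, 3 mg | s = 1 | s = 0.75 | s = 0.5 | s = 0.25 | Ratio |
|---|---|---|---|---|---|
| 5%, 20% | 15.0; 51% | 11.25; 39% | 7.5; 27% | 3.75; 15% | 4 throughout |
| 10%, 30% | 20.0; 59% | 15.0; 45% | 10.0; 30% | 5.0; 17% | 3 throughout |
| 10%, 40% | 30.0; 87% | 22.5; 72% | 15.0; 51% | 7.5; 27% | 4 throughout |

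Power is Φ[(Δ − 1.96·√(2p̄(1−p̄)/38)) / √((p₁(1−p₁)+p₂(1−p₂))/38)]. For 10% and 40% at s = 0.5, the recorded rates are 5% and 20%, so Δ = 0.15 and p̄ = 0.125. The null SE is 0.0759 and the alternative SE is 0.0739, giving z = (0.15 − 0.1487)/0.0739 = 0.02, or 51%. The SAP plans no formal test of AE rates. Power here only gauges how visible a dose effect would be.

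**5. Does variation between sites add to this?** With assumed rates of 10% and 40%, 5,000 simulated trials compared s fixed at 0.5 with s drawn uniformly between 0 and 1 for each of 40 sites. The mean recorded difference was 0.152 (fixed) and 0.150 (varying), with SD 0.074 and 0.075. Variation between sites added practically nothing beyond the average loss.

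**The case against.** The best defence is that Section 9.4.13 describes ordinary practice: an investigator always judges whether an observation is an AE, and the section says so. Injection-site reactions also have their own mandatory assessment at all seven dosing visits, on a fixed scale and on the CRF. Protocol 12.6 names them as a safety variable, SAP 6.6 tabulates them by arm, and SAP 2.2 promises subject-level listings from which a worst grade could be derived. Investigators are blinded, so equal under-recording leaves the ratio between arms intact.

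Much of this stands. Reactions seen at visits are not lost, and nothing shows that investigators would fail to file. Two things remain. Judgement without criteria does not fit a rule that all AEs are recorded, most plainly at Grade 3. And a listing is not a summary. The preserved ratio also needs equal recording by arm. If severe reactions were filed more readily and severity rose with dose (an assumption), recording would differ between arms even under blinding.

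A reader might infer several stronger points that the documents do not support:

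- **LISSA misses nearly everything.** The 7 visits are about 4% of 169 dosing days (7/169 = 4.1%), but that is a share of days, not of reactions. A visit assessment can show a reaction persisting from an earlier home injection, and extra LISSAs are allowed and reach the listings without an AE entry.
- **Site habit, rather than dose, drives the reported incidence.** With 152/40 = 3.8 subjects per site this is tempting, but step 5 does not bear it out.
- **Subject incidence shrinks in proportion to the filing rate per reaction.** A subject with five reactions, each filed independently with probability 0.3, is still counted with probability 1 − 0.7⁵ = 0.83.
- **An unfiled Grade 3 LISSA reaction escapes Section 8.3.** That section acts on TEAEs graded by CTCAE v5.0, while LISSA uses a different scale, and the documents do not map one to the other. What is shown is an unresolved link.

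**Conclusion.** The point holds as a possibility, not as a demonstrated bias. Sections 9.4.13 and 11.1 conflict on when an injection-site reaction is recorded as an AE, and the primary safety endpoint depends on the answer. It can therefore undercount a reaction the protocol already describes as dose-dependent. LISSA offsets this for reactions seen at visits, but the planned tables do not say how many subjects in each arm were ever affected.

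The size cannot be fixed from the documents. Under equal recording across arms, absolute rates and differences shrink by the factor s while ratios hold. If s is 1 there is no undercount at all. A reader might conclude that the endpoint does undercount, and does so differently by site; without any reporting rate, that does not follow. This is a modest defect, worth correcting because the main correction uses data already collected.

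**What to change.** **SAP 6.6.** Add, by treatment group in the safety analysis set, the number and percentage of subjects with any LISSA reaction, and the distribution of each subject's worst LISSA grade, over Day 1 to Week 24. Include unscheduled LISSAs as a stated exception to SAP 2.2. Because those extra assessments are themselves taken at the investigator's judgement, a row restricted to the 7 scheduled visits would be a useful check. Show these beside the TEAE tables so that a reader can see how far the two sources agree.

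**Protocol.** Reconcile Sections 9.4.13, 11.1 and 8.3 on when an injection-site reaction is recorded as an AE and on which scale it is then graded. Which rule should prevail is for the sponsor. Making every Grade 1 finding an AE is not requested: it would duplicate LISSA on a second scale and could interact with the TEAE-based rule in Section 8.3.

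**Cost.** One or two extra tables from data already on the CRF, and a short wording change. The SAP table is worth adding even if investigator discretion is kept.
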